### **8.7.3 Concomitant Medication Recording**

All medications (both prescription and non-prescription, and including vitamins, herbals, topicals, inhaled, and intranasal), taken during the screening period and throughout the trial, ending at the final protocol required visit, should be recorded on the appropriate eCRF. At each trial visit, subjects will be asked whether they have started or discontinued any medication since their previous trial visit. This includes single-use or as-needed medication use. Any medications taken within 30 days of a reportable event must be reported on the Concomitant Medication eCRF.

All medications and treatments, including vitamin supplements, over the-counter medications and oral herbal preparations must be recorded in the eCRFs. Routine medications and treatments used during each hemodialysis session, such as heparin injections or saline flushes, are not required to be recorded unless relevant for an AE or SAE. In addition, the ESA, blood transfusion, and iron treatment regimen prior to randomization and date of last dose will be recorded.

### **8.7.4 Vital Signs**

Vital signs will be collected at the time points described in the schedule of assessments ([Table 1.3-1](#)).

Vital sign measurements including temperature, heart rate, blood pressure, and respiratory rate will be assessed in the seated position after 5 minutes of rest prior to blood draws. For blood pressure, a total of 2 measurements at intervals of at least 2 minutes will be performed. Measurements will be taken prior to scheduled blood draws when possible.

### **8.7.5      *Electrocardiogram***

Electrocardiograms will be performed at the time points described in the schedule of assessments ([Table 1.3-1](#)).

A standard 12-lead ECG will be performed at Baseline, which may be obtained up to 3 days prior to the Baseline Visit. The ECG should be obtained after the subject has been resting comfortably in a supine position for approximately 5 minutes and should be taken prior to vital sign assessments and blood draws when possible. With the subject in a supine position, obtain the 12-lead tracing. All ECGs will be reviewed by the investigator for the presence of rhythms of potential clinical concern. A record of the tracing(s) will be made and retained with other source documents.

### **8.7.6      *Other Safety Variables***

#### **8.7.6.1      *Major Adverse Cardiovascular Events***

At each post-randomization trial visit, the subject must specifically be questioned regarding the occurrence of any potential MACE (all-cause mortality, nonfatal myocardial infarction, or nonfatal stroke) plus hospitalization for HF or thromboembolic event excluding vascular access thrombosis since the last trial visit. The eCRF must be completed in full at each visit even if no potential MACE (all-cause mortality, nonfatal myocardial infarction, or nonfatal stroke) plus hospitalization for HF or thromboembolic event excluding vascular access thrombosis events have occurred.

### **8.8      *Adverse Events***

AE collection will begin from time of signing the ICF through the Safety Follow-up Visit. The investigator and trial personnel will review each subject's laboratory and clinical evaluation findings and query the site directly regarding AEs (see [Section 8.8.1](#)). Subjects must be followed for AEs until the final required protocol visit or until all drug-related toxicities and SAEs have resolved (or are considered chronic/stable), whichever is later.

### **8.8.1 Definitions**

An AE is defined as any untoward medical occurrence (including an abnormal laboratory finding) in a clinical trial subject administered an IMP that occurs in the protocol-specified AE reporting period and which does not necessarily have a causal relationship with this treatment or usage. Adverse events would not include information recorded as medical history at Screening for pre-planned procedures for which the underlying condition was known and no worsening occurred. An adverse reaction is any untoward and unintended response to an IMP related to any dose administered.

An AE includes medical conditions, signs, and symptoms not previously observed in the subject that emerge during the protocol-specified AE reporting period, including signs or symptoms associated with pre-existing underlying conditions that were not present prior to the AE reporting period.

Adverse events therefore include the following:

- All AEs, whether suspected to be causally related to the IMP or otherwise.
- All AEs secondary to any medication overdose, medication error, abuse, withdrawal, sensitivity, or toxicity.
- Illnesses apparently unrelated to the IMP, including the worsening of a pre-existing illness (see paragraph below on Pre-existing Conditions).
- Injury or accidents. Note that if a medical condition is known to have caused the injury or accident (eg, a fall secondary to dizziness), the medical condition (dizziness) and the accident (fall) should be reported as 2 separate AEs.
- Abnormalities in physiological testing or physical examination findings that require clinical intervention or further investigation (beyond ordering a repeat [confirmatory] test).
- Laboratory abnormalities that require clinical intervention or further investigation (beyond ordering a repeat [confirmatory] test) unless they are associated with an already reported clinical event. Laboratory abnormalities associated with a clinical event reported as an AE (eg, elevated liver enzymes in a subject with jaundice) should be described under 'Comments' on the report of the clinical event rather than reported as separate AEs.

A suspected adverse reaction is any AE for which there is a reasonable possibility that the IMP caused the AE. For the purpose of Investigational New Drug (IND) safety reporting, "reasonable possibility" means there is evidence to suggest a causal relationship between the IMP and the AE. Suspected adverse reaction implies a lesser degree of certainty about causality.

Treatment-emergent AEs (TEAEs) are defined as AEs with an onset date on or after the start of open-label treatment. In more detail, TEAEs are all adverse events which started after start of open-label IMP treatment; or if the event was continuous from baseline and was worsening, serious, IMP related, or resulted in death, discontinuation, interruption or reduction of IMP.

The sponsor maintains and updates a listing of any adverse event of special interest (AESI), serious or non-serious, which is of scientific and medical concern specific to the sponsor's product or program, for which ongoing monitoring and rapid communication by the investigator to the sponsor could be appropriate.

A SAE includes any event that results in any of the following outcomes:

- Death.
- Life-threatening; Life threatening is defined as any event in which the subject was at risk of death at the time of the event; 'life-threatening' does not refer to an event which hypothetically might have caused death if it were more severe. For example, drug-induced hepatitis that resolved without evidence of hepatic failure would not be considered life threatening, even though drug-induced hepatitis of a more severe nature can be fatal.
- Persistent or significant incapacity/disability or substantial disruption of the ability to conduct normal life functions.
  - Disability is defined as a substantial disruption in a person's ability to conduct normal life functions.
- Requires inpatient hospitalization or prolongs hospitalization.
  - Hospitalization is defined as an overnight admission with observation of a minimum of 24 hours. A hospitalization planned before the start of the trial for a pre-existing condition that has not worsened during the AE reporting period does not constitute an SAE unless an untoward event occurs related to the procedure (eg, elective hospitalization for a total knee replacement due to a pre-existing condition of osteoarthritis of the knee that has not worsened during the course of the trial).
- Congenital anomaly/birth defect.
- Is considered a medically important event not meeting the above criteria, but which may jeopardize a subject, or may require medical or surgical intervention to prevent one of the criteria listed in this definition.

Serious also includes any other event that the investigator or sponsor judges to be serious. If there is any doubt whether the information constitutes an AE or SAE, the information is to be treated as an SAE.

In addition to the above criteria for classifying AEs as serious, **the following situations will also be classified as serious** for purposes of this trial:

- **Malignancies** – If a subject develops basal cell carcinoma of skin, squamous cell carcinoma of skin, or cervical carcinoma in situ during the trial, or has worsening of these events from baseline, the event will be reported as an SAE by the investigator. Newly diagnosed malignancies or a recurrence of a malignancy will be reported as an SAE with the seriousness criterion “medically important” if no other seriousness criteria are met.
- **Abnormalities in ALT or AST** – New elevations in ALT or AST  $> 3$  times ULN, with or without an elevation of total serum bilirubin  $> 2$  times ULN are to be reported to the sponsor’s Medical Monitor or CRO designee within 24 hours of awareness as an SAE with “medically important” criteria selected. The following steps are to be taken for subjects who experience new elevations in ALT or AST  $> 3$  times ULN, without an elevation of total serum bilirubin  $> 2$  times ULN:
  - Temporary interruption of IMP.
  - Repeat testing of ALT, AST, alkaline phosphatase (ALP), and total bilirubin, to be completed within 48 to 72 hours to confirm the abnormalities and to determine trend.
  - Trial medication should not be resumed until monitoring indicates abnormalities have resolved or are stable.

Nonserious AEs are all AEs that do not meet the criteria for a "serious" AE.

Clinical Laboratory Test Value Changes: It is the investigator’s responsibility to review the results of laboratory tests for each individual subject as they become available. This review will be documented by the investigator’s dated signature on the laboratory report. The investigator may repeat the laboratory test or request additional tests to verify the results of the original laboratory tests. If this laboratory value is considered medically relevant (ie, clinically significant) by the investigator (subject is symptomatic, requiring corrective treatment or further evaluation), or if the laboratory value leads to discontinuation, and/or fulfills a seriousness criterion, this is considered an AE.

Severity: Adverse events will be graded on a 3-point scale and reported as indicated on the eCRF. The severity of an adverse experience is defined as follows:

- 1 = Mild:** Does not interfere with subject's usual function.
- 2 = Moderate:** Interferes to some extent with subject's usual function.
- 3 = Severe:** Interferes significantly with subject's usual function.

Note that a severe AE is not necessarily a serious AE. For example, a headache may be severe in intensity, but would not be classified as serious unless it met 1 of the criteria for serious events listed above.

**IMP Causality:** The causal relationship of the AE to the IMP (vadadustat or darbopoetin alfa) will be assessed by both the investigator and the sponsor.

The assessment of causal relationship to the IMP should be evidence-based, and not based on the premise that all AEs are possibly causally related to the IMP until proven otherwise.

Examples of evidence that would suggest a causal relationship between the IMP and the AE include the occurrence of an AE that is uncommon and known to be strongly associated with drug exposure (eg, angioedema, hepatic injury, and Stevens-Johnson syndrome) or an AE that is uncommon in the population exposed to the drug.

The causal relationship of the AE is assessed using a binary system, and AEs are classified as either “related” or “unrelated” as follows:

**Related:** There is “reasonable possibility” that the drug caused the AE. The AE follows a reasonable temporal sequence from the time of drug administration. There is supportive evidence (facts) to suggest a possible causal relationship, irrespective of the degree of certainty between the observed AE and the drug.

**Unrelated:** An AE does not follow a reasonable temporal sequence from administration of the product and/or there is no reasonable possibility that the drug caused the AE. This assessment includes situations where the AE is related to other factors such as the subject’s clinical state, other therapeutic interventions, or concomitant drugs administered to the subject.

Default assessments using the ‘related’ category without supportive evidence for a causal relationship to the IMP is generally uninformative and do not contribute meaningfully to the development of the safety profile of the drug or to subject protection.

Investigators are encouraged to choose the most plausible cause for the event(s) from the following list: medical history, lack of efficacy/worsening of treated condition, IMP, other treatment (concomitant, or previous), withdrawal of IMP, administration error, protocol-related procedure, others (specify).

### **8.8.2 Eliciting and Reporting Adverse Events**

The investigator will regularly assess subjects for the occurrence of AEs. To avoid bias in eliciting AEs, subjects should be asked the nonleading question: “How have you felt since your last visit?” All AEs (serious and nonserious) reported by the subject must be recorded on the source documents and eCRF provided by the sponsor. Adverse event collection will begin from the time a subject signs the ICF.

Medical terminology should be used for AE reporting. Adverse events should be reported as a single unifying diagnosis whenever possible or, in the absence of a unifying diagnosis, as individual signs or symptoms.

**Exacerbation or disease progression** should be reported as an AE.

In addition, the sponsor must be notified immediately by telephone, fax, or e-mail. Special attention should be paid to recording hospitalization and concomitant medications.

Adverse event start date and time, end date and time, seriousness, severity, relationship to trial treatment (IMP Causality), action taken with trial treatment and outcome will be recorded on the source documents and in the eCRF.

#### **8.8.2.1 Guidelines for Reporting Adverse Events**

Each AE is to be classified by the investigator as SERIOUS or NONSERIOUS and all AEs (serious and non-serious) are to be reported on the AE eCRFs.

All AEs that occur in trial subjects during the AE reporting period specified in this protocol must be reported, whether or not the event is considered related to IMP (vadadustat or darbepoetin alfa). In addition, each trial subject will be questioned about AEs at each visit following the initiation of treatment as described in [Section 8.8.2](#).

The AE collection for this trial begins from time of ICF signing through the Safety Follow-up Visit.

In addition, any AE that occurs subsequent to the AE reporting period that the investigator assesses as related to the IMP should also be reported as an AE.

The following guidelines are to be used when reporting AEs for this trial:

**Medical Diagnoses** – Whenever possible, a medical diagnosis term should be used to report AEs instead of signs and symptoms due to a common etiology, as determined by qualified medical trial staff. For example, pneumonia should be the reported AE term, instead of fever and dyspnea, when the diagnosis has been established. Signs and symptoms should be reported as event terms only when the medical diagnosis remains unknown and revised to a medical diagnosis term once it has been established.

**Procedures** – Diagnostic and therapeutic non-invasive and invasive procedures, such as surgery, should not be reported as AEs. However, the medical condition for which the procedure was performed should be reported if it meets the definition of an AE. For example, an acute appendicitis that begins during the AE reporting period should be reported as the AE and the resulting appendectomy noted under “Comments”.

Pre-planned therapeutic procedures not associated with a new medical condition or worsening pre-existing condition should not be reported as AEs.

**Pre-existing Conditions** – In this trial, a pre-existing condition (ie, a disorder present before the AE reporting period started and noted on the pretreatment medical history/physical examination form) should not be reported as an AE unless the condition worsens or episodes increase in frequency during the AE reporting period.

**Abnormal Test Findings** – All laboratory test results will be reviewed by the investigator. The investigator will utilize his/her judgment in determining if out-of-range laboratory values are clinically significant (CS) and will denote this using the abbreviation “CS” on the laboratory report for source documentation. If there are significant changes in a laboratory report from a previous visit that are determined to be CS, these should also be reported as AEs. An expected laboratory abnormality from a condition that is part of the medical history is not considered CS for the purposes of the trial unless it represents a worsening of the condition.

**Abnormalities in ALT, AST, and Total Bilirubin** – Abnormalities in ALT, AST, and total bilirubin should be reported to the sponsor’s Medical Monitor or CRO designee within 24 hours of awareness as an SAE with “other medically important event” criteria selected, if the following conditions are met:

New elevation in ALT or AST  $> 3$  times ULN, with or without an elevation of total serum bilirubin  $> 2$  times ULN, and

If new elevations in ALT or AST  $> 3$  times ULN, without an elevation of total serum bilirubin  $> 2$  times ULN are identified, the following steps are to be taken:

- Temporary interruption of IMP;
- Repeat testing of ALT, AST, ALP, and total bilirubin, should be completed within 48 to 72 hours to confirm the abnormalities and to determine trend;
- Trial medication should not be resumed until monitoring indicates abnormalities have resolved or are stable.
- 

Details on the management of subjects with other ALT and AST abnormalities are further described in [Table 7.3.2-1](#).

**Worsening of Anemia** – In this trial, it is possible that some subjects may experience a worsening of anemia. As the primary endpoint of this trial assesses Hb response, worsening of anemia is captured as part of this efficacy parameter. Worsening of anemia should not be considered an AE unless the worsening of anemia is associated with a cause other than the subject’s CKD. However, if an event of worsening of anemia is due

to CKD and meets any serious criteria (see [Section 8.8.1](#)), it should be reported as an SAE.

**Transplantation** – During this long-term trial, it is anticipated that some subjects may receive a kidney transplant. These events will not be recorded as AEs. Subjects will discontinue IMP for receipt of a kidney, other solid organ, hematopoietic stem cell or bone marrow transplant and should continue with the Schedule of Assessments and safety assessments as described in [Section 7.3.2](#).

**Malignancy** – During this long-term trial, some subjects may develop a newly diagnosed malignancy or a recurrence of a malignancy. At the discretion of the investigator, these subjects may continue IMP (vadadustat or darbepoetin alfa). For reporting of AEs of malignancy, see [Section 8.8.1](#).

**Reporting MACE** – Investigators will be counseled to report any MACE (all-cause mortality, nonfatal myocardial infarction, or nonfatal stroke) plus hospitalization for HF or thromboembolic event excluding vascular access thrombosis events that they assess as requiring adjudication. All events will be submitted in a blinded fashion to the SEAC for adjudication. To protect the integrity of the trial, already adjudicated events will not be unblinded or reported to either Health Authorities or investigators as safety reports unless otherwise requested or required by Health Authorities or Ethics Committees. After trial completion, these events will be included in the final analysis which will be unblinded and submitted to Health Authorities with the trial report.

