### **6.3.2 Blinding**

This will be an open-label trial. Treatment assignment will be done through the IWR system and the investigator, sponsor, and contract research organization (CRO) trial teams will not be aware of which treatment will be assigned next. Treatments will be administered in an open-label fashion. The sponsor and CRO trial teams will be blinded to “by treatment” aggregated analyses except for the unblinded personnel. Because Hb values are objective and will be measured via a central laboratory for all efficacy endpoints, efficacy assessments are not considered to be subject to bias with an open-label design. In addition, the trial will involve the use of an IDMC, and an identical schedule of visits, procedures, and assessments for all treatment groups in order to reduce the potential for bias. Adjustments to doses for vadadustat will be based on Hb concentration and Dose Adjustment Algorithms and darbepoetin alfa will be based on USPI or EU SmPC.

As described in [Section 9.5](#), the Safety Event Adjudication Committee (SEAC) will remain blinded throughout the full course of the trial.

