### **8.8.2.2 Reporting Serious Adverse Events**

Any SAE, regardless of causal relationship, must be reported to the sponsor's Medical Monitor or CRO designee within 24 hours after the investigator becomes aware of the SAE. Compliance with this time requirement is essential so that the sponsor may comply with its regulatory obligations.

The initial SAE report should be completed as fully as possible but should contain, at a minimum:

- Subject number/identification, sex, and age/date of birth.
- The date of report.
- Name of the reporter.
- Name of the suspected medicinal product.
- A description of the event, including event term(s), seriousness criteria, and a clinical summary of the event.
- Causality assessment.

Information about all SAEs (either initial or follow-up information) should be collected and recorded in English on the electronic SAE Report Form within the electronic data capture (EDC) system. The investigator must assess the relationship to each specific component of the IMP. If the event meets serious criteria and it is not possible to access the EDC system, a paper SAE Report Form should be sent to the CRO via email or fax, or the investigator will call the CRO SAE hotline within 24 hours of being made aware of the SAE (reference the site manual for contact information). When the EDC system becomes available, the SAE information must be entered within 24 hours of the system becoming available.

The investigator must report follow-up information relating to an SAE to the sponsor's Medical Monitor or CRO designee within 24 hours of awareness updating the electronic eCRF with the new information or by submitting a paper SAE Report Form in the event that the EDC is not available. When the EDC system becomes available, the SAE information must be entered within 24 hours. The subject should be observed and monitored carefully until the condition resolves or stabilizes.

All deaths are to be thoroughly investigated and reported. Autopsy reports and death certificates are to be obtained, if possible.

The sponsor and/or its designee are responsible for reporting SAEs to all applicable regulatory agencies and the central ethics committees within the required timeline.

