10.4 Major Adverse Cardiovascular Event (MACE)

Potential safety events will be collected in Safety Event Data Collection eCRF page. The occurrence of any potential safety events will be summarized by SOC and PT for each treatment group, and a by-subject listing will be provided.

An independent Safety Event Adjudication Committee (SEAC) that is composed of independent experts will be formed prior to trial commencement to adjudicate the MACE (all-cause mortality, non-fatal myocardial infarction (MI), and non-fatal stroke) plus hospitalization for heart failure (HF) or thromboembolic event excluding vascular access thrombosis. Adjudicated safety events will be summarized for each treatment group, and a by-subject listing will be provided.

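### Protocol 8.8.2.1 lets unblinded investigators choose which potential MACE to report for adjudication, so referral of non-fatal events could differ by arm in a way that blinded adjudication cannot correct

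*Protocol*

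**What the plan says.** **Masking.** Protocol 6.3.2 states: "Treatments will be administered in an open-label fashion". The investigator therefore knows the arm. The same section says that "the Safety Event Adjudication Committee (SEAC) will remain blinded throughout the full course of the trial".

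**Capture.** Protocol 8.7.6.1 requires active questioning: "At each post-randomization trial visit, the subject must specifically be questioned regarding the occurrence of any potential MACE". It adds: "The eCRF must be completed in full at each visit even if no potential MACE" has occurred. SAP 10.4 says: "Potential safety events will be collected in Safety Event Data Collection eCRF page".

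**Referral.** Under Reporting MACE, Protocol 8.8.2.1 has investigators report events "that they assess as requiring adjudication. All events will be submitted in a blinded fashion to the SEAC for adjudication".

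**Remit.** Protocol 9.5 and SAP 10.4 say that the committee adjudicates MACE plus heart-failure hospitalization or thromboembolic events, excluding vascular access thrombosis. Neither mentions a choice by the investigator. Protocol 9.5 leaves further detail to a charter that is not among the documents.

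**Other reporting.** Protocol 8.8.2.2 requires that "Any SAE, regardless of causal relationship, must be reported to the sponsor's Medical Monitor or CRO designee within 24 hours" of awareness, and that "All deaths are to be thoroughly investigated and reported".

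**Analysis.** SAP 10.4 plans a by-arm summary of potential events by SOC and PT, and separately a by-arm summary of adjudicated events, each with a listing.

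**The concern.** Blinded adjudication protects the classification of an event once the committee has it. It cannot protect the step that decides whether the committee sees the event. Protocol 8.8.2.1 gives that step to someone who knows the treatment.

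Protocol 6.3.2 defends the open-label design on the ground that hemoglobin is objective and centrally measured. That argument does not extend to a decision on whether a suspected infarction, stroke or heart-failure admission should go to a committee. Protocol 2.1, 2.4 and 4.2 all stress the cardiovascular risk of ESAs, so investigators may hold expectations that differ by arm.

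At stake is the by-arm summary of adjudicated events, which Protocol 8.8.2.1 says will go to Health Authorities with the trial report.

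**Working it through.** **Step 1: follow an event through the text.**

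| Stage | Source | Depends on the investigator's opinion? |
|---|---|---|
| Subject questioned about potential events | Protocol 8.7.6.1 | No, mandatory at each visit |
| eCRF completed | Protocol 8.7.6.1; SAP 10.4 | Completion is mandatory |
| SAE or death reported to sponsor or CRO | Protocol 8.8.2.2 | Not on causality; no route to the committee is stated |
| Event reported for adjudication | Protocol 8.8.2.1 | Yes |
| Event classified | Protocol 6.3.2 and 9.5 | No, blinded committee |

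The sentence in 8.8.2.1 that sends all events to the committee follows directly on the filter. Its natural meaning is all events so reported; otherwise the filter would have no function. Neither document says that an entry on the safety-event page, an SAE or a death is forwarded automatically, and neither describes a central search of event terms.

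**Step 2: illustrate the size for non-fatal events.** The plan has no figure to reproduce. The true rate and the referral probabilities are assumptions. Only the arm size, about 100, comes from the documents.

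Let p be the true non-fatal risk, equal in arms A and B, and let r be the probability of referral. Adjudicated events per 100 = 100 × p × r. The apparent ratio B/A = r_B / r_A, so p cancels.

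With 12 true non-fatal events per 100:

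- 95% versus 80%: 12 × 0.95 = 11.4 and 12 × 0.80 = 9.6. Gap 1.8 events; ratio 0.80/0.95 = 0.84 (0.95/0.80 = 1.19 if the arms are reversed).
- 90% versus 85%: 12 × 0.90 = 10.8 and 12 × 0.85 = 10.2. Gap 0.6 events; ratio 0.85/0.90 = 0.94 (1.06 if reversed).

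Perfect classification of the referred events leaves these ratios unchanged.

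**Step 3: include deaths.** Suppose that a share f of all true events are deaths and that deaths are always referred (both assumptions). The ratio becomes [f + (1 − f) r_B] / [f + (1 − f) r_A].

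| f | 95% versus 80% | 90% versus 85% |
|---|---|---|
| 0.30 | 0.860/0.965 = 0.89 | 0.895/0.930 = 0.96 |
| 0.50 | 0.900/0.975 = 0.92 | 0.925/0.950 = 0.97 |

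**Step 4: compare with chance.** For counts a and b out of 100 each, SE(log ratio) = √(1/a − 1/100 + 1/b − 1/100).

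- 11.4 and 9.6: SE = 0.415, so the 95% interval around 0.84 is 0.37 to 1.90.
- 10.8 and 10.2: SE = 0.413, so the interval around 0.94 is 0.42 to 2.12.

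If p is varied from 10 to 20 per 100, the gap in the 95% versus 80% case is 1.5 to 3.0 events, and the interval around 0.84 runs from 0.34–2.07 to 0.46–1.54. All of these intervals include 1.

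**The case against.** The strongest reply has four parts.

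- **The filter may not operate in practice.** The remit in Protocol 9.5 and SAP 10.4 is unfiltered, capture is mandatory at each visit, and the charter may make referral automatic. This stands as a limit. A reader might infer that investigator selection is established as the only route to the committee, but the documents show only that it is the one route they describe. It does not remove the need to reconcile 8.8.2.1 with the other sections.
- **Selective referral would leave traces.** Potential events are to be summarized by arm. SAP 10.1 reports deaths by arm, and SAP 10.3 with Appendix D summarizes stroke, thrombosis and heart-failure terms by arm. None of this needs referral, and it stands as real mitigation. It is not complete: the proposed table list in SAP 19 has a table of adjudicated events (14.3.1.8) and a listing of reported events (14.3.2.6.1), but no summary table of potential events. A tabulation of raw reports also does not supply a missing adjudication.
- **The importance is modest.** A reader might infer that adjudicated MACE is the trial's cardiovascular result and that a formal comparison is biased. The documents do not support that. MACE is not named among the endpoints in Protocol Table 3-1 or SAP 7, SAP 10.4 plans a summary and listing with no ratio or margin, and the hierarchy in SAP 9.5 contains hemoglobin endpoints only. This part stands in full.
- **The illustrated gap is small.** It is under 2 events at 12 per 100, rests on assumed rates and lies within chance. This also stands. Chance variation does not make a systematic referral difference harmless, but in a trial of this size it would be hard to detect from the adjudicated counts alone.

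**Conclusion.** The concern holds in a limited form. Protocol 8.8.2.1 makes reporting for adjudication depend on an unblinded judgment, the statements of the committee's remit contain no such filter, and committee blinding cannot repair selection before referral. The exposure is mainly in non-fatal infarction, stroke, heart-failure hospitalization and thromboembolism, because all deaths must be reported.

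Under assumed referral of 95% versus 80% the apparent ratio is 0.84, and under 90% versus 85% it is 0.94. With deaths at 30% to 50% of events and always referred, these become 0.89–0.92 and 0.96–0.97. The bias could go either way. A reader might infer that referral will differ, or that it favors one drug; nothing in the documents shows either. The hemoglobin analyses are unaffected. This is a cheap improvement to a descriptive safety summary, not a threat to the trial's main conclusions.

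**What to change.** 1. In Protocol 8.8.2.1, delete the clause that makes reporting depend on the investigator's view of whether adjudication is needed. Align the text with Protocol 9.5, SAP 10.4 and the charter. If the charter already contains an automatic trigger, say so in the protocol.
2. Send the committee every death, every entry on the Safety Event Data Collection page, and every AE or SAE found by a treatment-blind search on a pre-specified term list.
3. Build that list from SAP Appendix D only after editing it. The thrombosis list there includes vascular-access, fistula, graft, shunt and device terms; remove them, since the adjudicated endpoint excludes vascular access thrombosis. Add pulmonary embolism, which is absent, and any other missing in-scope terms.
4. Tabulate by arm the events identified, referred and confirmed.

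The cost is protocol and charter wording, a simple search of terms that are already MedDRA-coded, and some extra dossiers for the existing committee. Because unblinded sites still write the event terms, the change reduces the bias path but does not eliminate it.
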